A prospective, randomized clinical trial to compare vestibular incision supraperiosteal tunnel access (VISTA) and sulcular tunnel access root coverage procedures with coronally advanced flap and acellular dermal matrix (ADM) to treat teeth with gingival recession and lack of adequate keratinized tissue. A pilot study.

Study Protocol & Statistical Analysis Plan

NCT03566108

August 31, 2022

[name], MS, Principal Investigator

University of Alabama at Birmingham
Birmingham, AL 35294

A prospective, randomized clinical trial to compare vestibular incision suprapariosteal tunnel access (VISTA) and sulcular tunnel access root coverage procedures with coronally advanced flap and acellular dermal matrix (ADM) to treat teeth with gingival recession and lack of adequate keratinized tissue. A pilot study.

1. Study Protocol 1. Objectives/Specific Aims:

This investigator-initiated study will compare two commonly used soft tissue grafting techniques [vestibular incision suprapariosteal tunnel access (VISTA) vs. sulcular tunnel access root coverage procedures with the uses of acellular dermal matrix (ADM)] to achieve coronal flap advancement and root coverage as well as augmentation of soft tissue at intraoral tooth sites. Research data and daily clinical observations reveal that teeth with gingival recession and a lack of adequate keratinized tissue (KT) are more prone to persistent gingival inflammation, dentinal sensitivity, radicular (root) caries (tooth decay), faster periodontal attachment loss, and compromised plaque control. Soft tissue grafting (by various techniques) aims at changing the quality, quantity and placement of the soft tissue around teeth by covering exposed root surfaces and creating or increasing the zone of keratinized mucosa (KM) surrounding the affected teeth. Both techniques tested have shown good clinical outcomes with regard to root coverage, but clinical reports of the VISTA technique and other similar techniques suggest that patients experience a decrease in site morbidity and discomfort post-operatively. To our knowledge, these 2 types of grafting techniques have not been compared in a prospective trial for differences in clinical (percentage of root coverage, amount of KT increase, tissue thickness increase, and practitioner-assessed esthetics) and patient-centered outcomes (pain, swelling, change in daily activities, and patient-assessed esthetics) in a controlled study.

2. Materials and Method:

Study population:

A total of 40 patients seeking treatment at the UAB SOD Graduate Periodontology clinics will be recruited to participate in this study. The potential candidates will be approached during the treatment planning and/or pre-surgical visit in the periodontal clinic. The investigator/research staff will give the IRB approved consent form to the potential participants, explain the study, and obtain the patient demographics if the patient participate in the study.

Procedures:

Normal dental appointment: Patients that are seen at the school of dentistry for regular dental care and evaluation may be identified as plausible participants for the study based on the inclusion criteria, they will be scheduled for a screening appointment to determine eligibility for inclusion within the study. Screening/baseline visit: patient's electronic records will be reviewed to assess radiographic documentation. If the x-ray is at least one year old a new radiograph will be obtained. Two trained and calibrated examiners will conduct clinical and radiographic evaluations to determine eligibility according to the above criteria. Study visits and objectives will be explained to all participants. IRB approved written informed consent will be obtained from all the participants. Photos will be obtained at the screening visit and at each subsequent visit (1-7) to evaluate healing of the tissue.

Clinical parameters that will be captured include:

- Probing depth (PD) measurements
- Bleeding on probing (BOP)
- Plaque Index (PI, Silness & Loe): A modification of the Silness and Loe Plaque Index will be used full mouth. Categories 2 and 3 from the original index will be collapsed into a single

category so that examiners only have to distinguish between visible plaque and plaque that cannot be seen but is detectable with the probe. A single score will be recorded for each tooth. A single score 0 to 2 will be recorded for buccal and lingual/palatal surface of each tooth examined as follows:

0 = No plaque

1 = A film of plaque adhering to the free gingival margin and adjacent area of the tooth which cannot be seen with the naked eye. But only by using disclosing solution or by using probe.

2 = Moderate accumulation of deposits within the gingival pocket, on the gingival margin and/or adjacent tooth surface, which can be seen with the naked eye.

- Gingival Index (*GI*, Loe and Silness) at surgical site(s). A periodontal probe will be swept around the tooth sulcus at a depth of 1-2 mm. The examiner will determine the status of tissue health. A single score will be recorded for buccal and lingual/palatal surface of each tooth examined as follows:

0 = healthy tissue

1 = mild inflammation but no bleeding

2 = moderate inflammation with bleeding

3 = severe inflammation with a tendency toward spontaneous bleeding

- Width of keratinized tissue (KT) will be measured at tooth site(s) at the mid-buccal aspect from the mucosal margin to the mucogingival junction.
- Width of attached tissue (AT) will be calculated by subtracting PD from KM
- Tissue Thickness (TT1 and TT2) at the buccal mucosa will be measured during the surgical visit by horizontal transmucosal probing (sounding the bone) using an endodontic reamer after local infiltration of anesthetic prior to surgical site preparation. TT1 and TT2 will be measured at 2 mm and 5 mm from the mucosal margin, respectively.

Clinical photographs of the tooth site (s) will be obtained with one digital SLR camera.

Randomization: two groups (Participants will be randomized like the flip of a coin to one of the two groups listed.) Randomly generated treatment groups will be printed on note cards and placed in sealed opaque envelopes. Once the patient consents to participate in the study an envelope is opened, and the patient is then offered the allocated treatment regimen.

Group 1: will receive vestibular incision supraperiosteal tunnel access (VISTA) + Acellular Dermal Matrix (ADM) graft around teeth with gingival recession and lack of KT.

Group 2: will receive sulcular tunnel access + Acellular Dermal Matrix (ADM) graft around teeth with gingival recession and lack of KT.

Surgical visit (Visit 1): Patients will be anesthetized via infiltration around recipient tooth/teeth site(s). Study surgeon will confirm measurements taken at baseline with relation to width of keratinized tissue (KT) and evaluate thickness of mucosa (TT1 and TT2) as described above. Surgeon will then measure the recipient site to determine the size of graft needed and ensure that surgical treatment will avoid any vital structures. Soft tissue grafting procedures will include local anesthesia, monitoring of vital signs (bp, HR, O2 sat). Study surgeons will follow standard-of-care procedures for soft tissue as follows:

- Group 1: vestibular incision suprapariosteal tunnel access (VISTA) + Acellular Dermal Matrix (ADM)

The tooth/teeth site(s) will be prepared utilizing a vertical vestibular incision beyond the mucogingival junction and split-thickness flap elevated on buccal aspect leaving a thin periosteum as recipient bed. Extension of the flap to the gingival margin and laterally to allow for adequate coronal advancement and coverage of the ADM graft material will be insured. Mesio-distal and apico-coronal dimensions will be measured at recipient site the ADM material trimmed after hydration and washing per package instruction to equal dimensions and uniform thickness will be performed. Exact AMD graft dimensions will be measured with a calibrated UNC-15 periodontal probe and its thickness will be measured using a caliper prior to placement within the suprapariosteal pouch at the recipient site. ADM graft will be secured in position and overlying flap secured in a coronal position with multiple suture techniques.

VISTA procedure:

	
Pt. presents with Miller Class I & II recession defects on upper front teeth.¹²

	
Midline incision made and tissue released.¹²

	
Release extended to include all involved teeth.¹³

	
Acellular Dermal Matrix (ADM) is guided and manipulated to cover all root surfaces.¹²

	
Tissue is repositioned at the desired level. Sutures bonded to the front of each tooth.¹²

	
Midline incision sutured.¹²

	
12 month follow up appt.¹²

- Group 2: sulcular tunnel access + Acellular Dermal Matrix (ADM) graft

The tooth/teeth site(s) will be prepared utilizing a papilla-sparing, sulcular incision extending one tooth mesial and distal to the tooth/teeth site(s) to be treated and split-thickness flap elevated on buccal aspect leaving a thin periosteum as recipient bed. Extension of the flap apically and laterally to allow for adequate coronal advancement and coverage of the ADM graft material will be insured. Mesio-distal and apico-coronal dimensions will be measured at recipient site the ADM material trimmed after hydration and washing per package instruction to equal dimensions and uniform thickness will be performed. Exact AMD graft dimensions will be measured with a calibrated UNC-15 periodontal probe and its thickness will be measured using a caliper prior to placement within the suprapariosteal pouch at the recipient site. ADM graft will be secured in position and overlying flap secured in a coronal position with multiple suture techniques.

Table 2: Tunneling and ADM technique

	
Pt. presents with Miller Class II and III recession defects.

---	---

	
Incision made on the front of each tooth to be treated.

	
Elevation of the flap with blunt dissection to necessary level.

	
Insertion of acellular dermal matrix.¹⁵

	
Positioning of acellular dermal matrix with sutures overlying root surfaces.

	
Flap positioned at the desired level and sutured into place.

	
One month post-operative evaluation of healing.

To help guard against possible infection, a pre-surgical antibiotic loading dose will be dispensed and prescriptions for relief of post-surgical discomfort, follow-up antibiotics and written home care instructions will be provided.

Follow up visits: The surgical sites will be examined at 1 week (visit 2) and 2 weeks (visit 3) after surgical visits and loose sutures will be removed. Exams will then be scheduled at 1 month (visit 4), 3 months (visit 5), 6 months (visit 6), and 1 year (visit 7).

During these follow up visits the following will take place:

1. Medical history review (all visits)
2. Assess for adverse events experience (all visits)
3. Intra-oral photographs: (all visits)
4. Clinical measurements:
The width of keratinized tissue (KT) will be assessed at visits 4, 5, 6 and 7. Tissue thickness (TT1 and TT2) will be evaluated at visits 5, 6 and 7. Clinical measurements will be collected by calibrated examiners. Measurements from all visits will be compared to baseline in order to evaluate the progression of healing over time up to 12 months post-op.
5. Patient satisfaction survey
This survey will be performed at visits 2 and 4 using a visual analogue scale (VAS) based questionnaire regarding esthetic appearance, pain, swelling, bruising, effects on daily activities. Esthetic evaluation by the patient will also be assessed at visits 6 and 7.
6. Pink Esthetics Score (PES)
This standardized assessment of esthetics will be performed at visits 6 and 7 by blinded, calibrated examiners.
7. Study participation and satisfaction survey to be completed at final study visit (visit 7)

Inclusion/Exclusion Criteria:

Inclusion Criteria	Exclusion Criteria
English speaking	Non-English speaking
At least 18 years old	Less than 18 years old
Must be a patient of the UAB Dental School	Smokers/tobacco users (>10 cigarettes/day)
Able to read and understand informed consent document.	Patients with systemic pathologies or conditions contraindicating oral surgical procedures or adversely affecting wound healing.
One or more adjacent teeth (up to four) with Miller class I or II gingival recession defects and ≤ 2mm of KT at each site to be treated.	Presence of active periodontal disease or radiographic interproximal bone loss or tooth malposition, which would yield a Miller class III or IV categorization for the recession defect.
Presence of periodontally healthy, non-carious neighboring teeth, healthy implants, or edentulous ridges on either side of the involved site(s)	Presence of frenulae or other soft tissue anomalies at the site(s) to be treated that, in the opinion of the investigators, will interfere with successful access and treatment of the soft tissue defects.
No anticipated need for restorative care at the teeth to be treated during the study period.	Previous soft tissue grafting at the site(s) to be treated

--	--

Group Table:

Group	Treatment	Number of participants
Group 1	Vestibular incision suprapariosteal tunnel access (VISTA) + Acellular Dermal Matrix (ADM) graft	20
Group 2	Sulcular tunnel access + Acellular Dermal Matrix (ADM) graft	20

3. Study Background:

Soft tissue grafting for root coverage and alteration of the quality of gingival tissue surrounding teeth was originally described in 1956 using a Lateral Pedicle Flap.¹ Since that time, myriad techniques and materials have been described to improve clinical outcomes and patient acceptance.²⁻⁶ Systematic reviews and meta-analyses have concluded that root coverage and KT gain at sites with Miller class I or II defects could be reliably achieved with the use of allogeneic donor tissue as well as autogenous connective tissue harvested from a patient’s palate.⁷⁻⁹ Use of a tunnel technique has also been shown to demonstrate decreased post-operative discomfort when compared with a standard coronally advanced flap.¹⁰ Recently, there has been renewed interest in vestibular incisions, originally described in 1912¹¹, for the coronal advancement of gingival tissues with the use of graft materials due to purported decrease in post-operative discomfort and healing time.

Given the increase in the number of procedures performed, this study seeks to compare two established tunneling technique procedures with the use of allogeneic soft tissue graft materials to evaluate clinical and patient-centered outcomes to determine if there are any notable differences in post-operative healing and clinical outcomes associated with each technique.

4. Outcomes Measures

Outcomes will be measures by an evaluation of the following:

- Percentage previously visible root surface that has been covered by gingiva at 6- and 12-months following grafting with VISTA and sulcular tunnel access with ADM as compared to the baseline data.
- KT width as measured in mm by practitioner at 6- and 12-month following grafting with VISTA and sulcular tunnel access with ADM
- Change in tissue thickness evaluated with gentle intrasulcular probing and level of transparency of the grafted sites at 6 and 12 months.
- Practitioner-assessed esthetic outcomes using a standardized pink esthetic scale (PES) at 6 and 12 months postoperatively.
- Patient-assessed esthetic outcomes of root coverage and soft tissue appearance at 6 and 12 months post-operatively
- Patient centered outcomes including pain, bleeding, swelling, change in daily activities at 1 week and 1 month postoperatively, see attached Visual Analog Scale (VAS)
- Group sample sizes of 20 and 20 achieve 92% power to detect non-inferiority using a one-sided, two-sample t-test. The margin of non-inferiority is -1.0. The true difference between the means is assumed to be 0.1. The significance level (alpha) of the test is 0.025. The data are drawn from populations with standard deviations of 1.0 and 1.0.

- Regarding patient-centered outcomes, there is not adequate data available to complete an accurate sample size analysis to determine the proper N, therefore in this respect this study serves as a pilot study.

5. Benefits:

Benefits of this project for individual participants include enhancing periodontal soft tissue health and thus decreasing the risks of dentinal sensitivity, radicular (root) caries (tooth decay), and tooth root structure wear as well as a reduction in progressive recession and periodontal attachment loss at the tooth sites to be treated. Information gained from this research may be used by investigators to facilitate a healthier environment around teeth with gingival recession and a lack of keratinized tissue (KT) with therapies that are well-accepted with low post-operative morbidity.

6. Risks

The only risks associated with this protocol involve potential loss of confidentiality and randomization. Precautions will be taken to ensure that patient confidentiality is maintained. All records will be assigned identifying alphanumeric codes and the list linking identifying PHI to patient data will be kept on a password protected computer and destroyed immediately after statistical analysis is completed. All surveys and consent documents will have assigned non-identifying, alphanumeric codes and the list linking personal information and patient data will be kept on a password protected computer and destroyed immediately after data analysis have been completed. Intra-oral photos will also be assigned alphanumeric codes that link with codes assigned to the demographic data collection form and consent documents. Photos will be stored as digital images on encrypted computers in the department of Periodontology. The photos will be used in the publication and presentations.

Regarding the randomization risk, patients will be assigned to a group by chance, which may prove to be less effective than the other. Both surgical techniques to be tested have been shown to result in clinical improvements in root coverage and soft tissue quality. There is a chance that one procedure may have a risk of increased post-operative discomfort, although there is considerable variability in patient reported discomfort after having received the same treatment with either group.

Regarding procedural risks, due to each subject's physical and dental conditions being unique, the success of tissue grafting cannot be guaranteed. Some discomfort after treatment can be expected. This may include pain, bleeding, inflammation, and soreness. These discomforts can be expected to go away within approximately 48 hours. The treatment site could become infected. If an infection occurs, the study dentist will treat the area.

Risks associated with use acellular dermal matrix (both groups) include a low, theoretical possibility of viral or prion contamination of the materials. No such contamination has ever been reported and ADM has been used in many medical and dental applications. ADM is processed from cadaveric donor skin and all donors are tested for nondetectable levels of HIV and HepC. Furthermore, it is processed using proprietary methods to removal all cells and cellular components (and this is histologically verified for each processing batch) to allow the collagenous and extracellular framework to remain without the cells which may produce antigenicity.

Risks associated with dental anesthesia include injury to nerves, which may cause numbness or tingling of the lips, other teeth, chin, face, and tongue. This is usually temporary but could be permanent. The mouth, lips and tongue may remain numb for up to four hours after the treatment. During this time there may be difficulty eating, drinking, speaking, and smiling.

Some subjects may experience sensitivity or allergy to the anti-bacterial mouth rinse, the local anesthesia, the antibiotics given, or the post-treatment medications prescribed.

A major side effect of the anti-bacterial mouth rinse is staining of the teeth. This stain is similar to stains left by coffee or tea, or by smoking and may be removed by professional teeth cleaning. A less

frequent side effect may include temporary changes in taste. This will disappear once use of the rinse is stopped.

There may be other risks that are unknown.

7. Confidentiality

Data will be stored in a password-protected study-specific computer database within the department of Periodontology. Photographs of the teeth and gums will not be individually identifiable. The computer is backed-up by UAB IT. Knowledge of passwords and access to the database will be strictly limited to study personnel who are working with the collected data.

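### The plan does not say how one to four teeth per randomized patient enter the analysis; the only named test assumes independent values and would exceed its 2.5% error if run on teeth.

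*Combined protocol and SAP*

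**What the plan says.** The combined protocol and SAP randomizes people (section 2, Randomization): "Participants will be randomized like the flip of a coin to one of the two groups listed". Section 2, Study population, gives the total: "A total of 40 patients seeking treatment at the UAB SOD Graduate Periodontology clinics will be recruited to participate in this study". The Group Table lists 20 participants in each group.

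The inclusion criteria allow several teeth per person: "One or more adjacent teeth (up to four) with Miller class I or II gingival recession defects". Section 2 then defines the KT reading: "Width of keratinized tissue (KT) will be measured at tooth site(s) at the mid-buccal aspect from the mucosal margin to the mucogingival junction". A mid-buccal reading exists once per tooth, so a patient with four treated teeth yields four KT values at each assessment.

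The only statistical test in the document is in the sample-size bullet of section 4: "Group sample sizes of 20 and 20 achieve 92% power to detect non-inferiority using a one-sided, two-sample t-test". The same bullet sets the margin at −1.0, takes 0.1 as the true difference, uses a one-sided alpha of 0.025, and assumes a standard deviation of 1.0 in each group. It names no outcome for the margin and does not say whether the standard deviation is per tooth or per patient. No section gives a unit of analysis, a rule for combining teeth, an index tooth, an intra-patient correlation or an adjustment for clustering.

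**The concern.** Teeth in one mouth, side by side, treated in one surgical procedure, cannot be presumed independent. A two-sample t-test treats every value it receives as independent. Given tooth values, it counts between 40 and 160 observations (40 patients × 1 to 4 teeth) where only 40 units were randomized. Its standard error is then too small whenever teeth in the same patient are positively correlated, and patients with more teeth carry more weight.

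In a non-inferiority comparison, an interval that is too narrow leads to claiming non-inferiority too often when the true difference sits at the margin. The silence also leaves a choice open. All teeth, the mean tooth, the worst tooth or one chosen tooth are each compatible with the text and can give different answers. If that choice is made after the data are seen, the conclusion can depend on it.

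**Working it through.** **1. The plan's own figure.** Inputs from the sample-size bullet: 20 per group, margin −1.0, true difference 0.1, SD 1.0, one-sided alpha 0.025.

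- Distance from the margin: 0.1 − (−1.0) = 1.1.
- Standard error: 1.0 × √(2/20) = 0.316.
- Non-centrality: 1.1 / 0.316 = 3.48; df = 38; critical t = 2.024.
- Power from the non-central t: **92.4%**, against 92% stated.

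The figure reproduces with 20 + 20 independent units, which is the number of participants in the Group Table.

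**2. Error of the t-test if tooth values were used.** With m teeth per patient and within-patient correlation ICC, the variance of the group difference is larger than the test assumes by the design effect

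DE = 1 + (m − 1) × ICC,

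and the true one-sided error at the margin is approximately

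1 − Φ(1.96 / √DE).

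The documents give neither ICC nor the distribution of teeth, so both are varied. Example: m = 2, ICC = 0.3 gives DE = 1.3, 1.96/√1.3 = 1.72, error 4.3%.

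| Teeth in every patient | ICC 0.1 | ICC 0.3 | ICC 0.5 | ICC 0.7 |
|---|---|---|---|---|
| 1 | 2.5% | 2.5% | 2.5% | 2.5% |
| 2 | 3.1% | 4.3% | 5.5% | 6.6% |
| 3 | 3.7% | 6.1% | 8.3% | 10.3% |
| 4 | 4.3% | 7.8% | 10.8% | 13.3% |

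**3. Mixed numbers of teeth.** When patients differ, replace m by Σm²/Σm.

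- One to four teeth equally likely: (1 + 4 + 9 + 16)/(1 + 2 + 3 + 4) = 3, so the formula gives the three-teeth row above.
- Mostly single teeth (70% one, 20% two, 7% three, 3% four): 2.61/1.43 = 1.83.

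These were checked by simulation: 20 + 20 patients, normal outcomes, exchangeable correlation, no dropout, 40,000 runs per setting, pooled t-test on teeth.

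| Tooth mix | Method | ICC 0.1 | ICC 0.3 | ICC 0.5 | ICC 0.7 |
|---|---|---|---|---|---|
| 1–4 equally likely | formula | 3.7% | 6.1% | 8.3% | 10.3% |
| 1–4 equally likely | simulation | 3.7% | 6.0% | 8.6% | 10.6% |
| 70% one tooth | formula | 3.0% | 4.0% | 5.0% | 5.9% |
| 70% one tooth | simulation | 2.9% | 3.8% | 4.9% | 6.0% |

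**4. One value per patient.** In the same simulations, a t-test on each patient's mean over treated teeth had error of 2.4% to 2.7% in every setting, including unequal numbers of teeth. The mixed model proposed below was not simulated.

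**The case against.** The strongest reply is that the plan never proposes a tooth-level test. The sizes of 20 and 20 in the power sentence match the Group Table's participants, so the t-test as written reads as patient-level, and its power is right on that basis. This stands. A reader might infer that the trial will analyse up to 160 teeth as independent, or that the 92% is wrong; the documents support neither. What the reply does not supply is the step from several KT values to one value per patient, and a patient-level sample size does not define that step.

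A reader might also quote the inflation as a flat two- to four-fold. That depends on inputs the documents lack. It is about right at ICC 0.5 with two to four teeth in every patient (5.5% to 10.8%, or 2.2 to 4.3 times 2.5%). There is no inflation if every patient has one tooth, and little if most do and the correlation is low.

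Third, the documents do not show every clinical outcome to be recorded per tooth. KT is the clear case. Tissue thickness is taken at the buccal mucosa with no explicit per-tooth statement. Percentage root coverage is listed as an outcome in section 4, but no recession or root-coverage measurement appears among the captured clinical parameters in section 2. These objections limit how the point may be stated; they do not remove it.

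Finally, one mean per patient holds the error rate and fits the named test and sample size, so it is not inferior to a mixed model on that ground. That is accepted in the fix.

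**Conclusion.** The point holds as an omission with a conditional consequence: the unit of analysis and the handling of several teeth per patient are not specified, and the one named test makes no allowance for clustering. If it were applied to teeth, the one-sided 2.5% error would be about 3–4% at ICC 0.1 under the two mixed-tooth scenarios, or at ICC 0.3 with mostly single-tooth patients. It would be about 6% to just over 10% with one to four teeth equally likely and ICC 0.3 to 0.7.

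These figures rest on assumed correlations and tooth mixes, normal outcomes and no dropout. They do not depend on which outcome the margin belongs to, because the error rate at the margin is free of scale. The 20 + 20 and the 92% need no change, provided the SD of 1.0 is that of one value per patient. The matter deserves correction before analysis because the error control depends on a choice the plan leaves open.

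**What to change.** In section 4, state that the patient is the unit of inference, and name one of two analyses for KT and tissue thickness before outcome data are seen:

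- a linear mixed model on tooth values, with arm, the tooth's own baseline value, a random intercept for patient, and small-sample degrees of freedom (Kenward-Roger or Satterthwaite); or
- one mean per patient over the treated teeth, compared between arms with adjustment for the patient's mean baseline value.

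Either uses all treated teeth and avoids an after-the-fact choice of tooth. Treat percentage root coverage in the same way, with patient clustering or one value per patient, but without a recession-baseline covariate unless recession is recorded. It would also help to say that the SD of 1.0 is the patient-level SD.

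For KT and tissue thickness this needs no new patients, visits or measurements. The cost is slightly more analysis work and intervals wider than a tooth-level t-test would show.

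### Baseline tissue thickness is sounded after anesthetic infiltration, but nothing requires the same method and tissue condition at follow-up, so change from baseline may subtract non-comparable readings.

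*Combined protocol and SAP*

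**What the plan says.** Three parts of the combined protocol and SAP bear on this outcome.

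- **Section 2, clinical parameters (Tissue Thickness) and Visit 1.** TT1 and TT2 are read at 2 mm and 5 mm from the mucosal margin by transmucosal bone sounding at the surgical visit, "using an endodontic reamer after local infiltration of anesthetic prior to surgical site preparation". The Visit 1 text starts with infiltration around the teeth to be treated, in one sentence that serves both arms. It then has the study surgeon "evaluate thickness of mucosa (TT1 and TT2) as described above". This is the only baseline thickness reading described. No injected volume, waiting time or pre-injection reading is given.
- **Section 2, follow-up visits, item 4.** "Tissue thickness (TT1 and TT2) will be evaluated at visits 5, 6 and 7", that is, at 3, 6 and 12 months. "Measurements from all visits will be compared to baseline in order to evaluate the progression of healing over time up to 12 months post-op". The anesthetic condition at these visits is not stated.
- **Section 4, Outcomes Measures.** The outcome is "Change in tissue thickness evaluated with gentle intrasulcular probing and level of transparency of the grafted sites at 6 and 12 months". This is a different method from bone sounding.

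On allocation, section 2 says: "Once the patient consents to participate in the study an envelope is opened". The arm is therefore known before Visit 1.

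**The concern.** A change score is interpretable only if its two readings measure the same thing in the same condition. Here the baseline is taken in recently infiltrated tissue, and injected fluid occupies volume where thickness is sounded. Eligibility requires 2 mm or less of keratinized tissue, so TT2, at 5 mm from the margin, lies at least 5 - 2 = 3 mm beyond the keratinized zone at baseline. That follow-up is read in the same condition is nowhere required, and section 4 points to another method altogether.

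Two things are at stake. The first is the gain within each arm, because any distension present only at baseline is subtracted from it one for one. The second is precision, because distension that varies from patient to patient adds variance to every change score. Increase in tissue thickness is one of the clinical outcomes that section 1 says the trial will compare.

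**Working it through.** **1. The plan's own figure.** Section 4 gives 20 per group, margin -1.0, true difference 0.1, SD 1.0 and one-sided alpha 0.025. The distance to the margin is 0.1 - (-1.0) = 1.1. The noncentrality is 1.1 / (1.0 × √(2/20)) = 3.48 on 38 degrees of freedom, and the power is 92.4%. The stated 92% reproduces. The endpoint is not named, so 1.0 is the only SD available and may not be a thickness SD.

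**2. Effect on the gain within an arm.** Let b be the mean distension at baseline and f the mean distension at follow-up.

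observed gain = true gain - b + f

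The documents give neither b nor f, so the values below are assumptions.

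| True gain (mm) | b (mm) | f (mm) | Observed gain (mm) |
|---|---|---|---|
| 0.50 | 0.3 | 0 | 0.20 |
| 0.50 | 0.5 | 0 | 0.00 |
| 0.50 | 0.3 | 0.3 | 0.50 |

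For scale, thickening = retained volume / area. An assumed 0.05 mL over 2 cm² is 50 mm³ / 200 mm² = 0.25 mm. Volumes of 0.02 to 0.10 mL over 1 to 4 cm² give 0.05 to 1.0 mm. That range is too wide to settle the size. It shows only that the effect need not be negligible.

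**3. Effect on the comparison of arms.**

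observed difference = true difference - (b₁ - b₂) + (f₁ - f₂)

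With b₁ = b₂ and f₁ = f₂ the shift drops out. A simulation with true gains of 0.6 and 0.5 and a common baseline-only swelling of 0.3 or 0.5 left the difference at about 0.10.

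**4. Noise.** Distension with between-patient SD s at baseline raises the variance of change from SD² to SD² + s².

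| Assumed SD of change (mm) | s = 0.2 mm | s = 0.3 mm |
|---|---|---|
| 0.4 | (0.16 + 0.04) / 0.16 = 1.25 | (0.16 + 0.09) / 0.16 = 1.56 |
| 0.5 | (0.25 + 0.04) / 0.25 = 1.16 | (0.25 + 0.09) / 0.25 = 1.36 |
| 1.0 (stated SD, endpoint unnamed) | 1.04 | 1.09 |

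If the SD of 1.0 did apply to thickness change, power would fall from 92.4% to 91.4% (s = 0.2) or 90.1% (s = 0.3).

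**5. Change score against baseline as a covariate.** Assume a true-thickness SD of 0.4 mm at each visit, a correlation of 0.5 and a baseline error SD of 0.3 mm.

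- Change: variance = 2 × 0.16 × (1 - 0.5) + 0.09 = 0.25. SE of the arm difference = √(0.25 × 2/20) = 0.16 mm.
- Covariate: slope = (0.5 × 0.16) / (0.16 + 0.09) = 0.32. Residual variance = 0.16 - 0.08² / 0.25 = 0.134. SE = √(0.134 × 2/20) = 0.12 mm.

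On these inputs, an arm-specific distortion of the baseline would enter a change score in full, but a covariate analysis at only 0.32 of its size. It would be reduced but not removed.

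**The case against.** Bone sounding may well need anesthesia, so reading after infiltration is not itself a mistake. Item 4 of the follow-up text also reuses the labels TT1 and TT2 without a new method. The natural reading is that the same procedure, infiltration included, is repeated. If so, the mean change is unbiased and only noise is left. That is a fair reading of item 4 alone. It does not settle the matter, because section 4 gives a different method for the same outcome and no section states the follow-up condition.

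A reader might go further and infer that infiltration differs by arm, since allocation is known and the two incisions enter through different tissue, and so produces a false technique effect. With SD 0.4 to 0.5 mm and a two-sided 5% test, arm differences in distension of 0.1, 0.2 and 0.3 mm would give false-positive rates of about 10 to 12%, 23 to 34% and 46 to 64%. At the stated SD of 1.0 they would be 6.1%, 9.5% and 15.2%. The documents do not support this reading. One infiltration sentence covers both arms, both arms raise a split-thickness buccal flap, and no volume, placement or difference is given. The plan also specifies no two-sided test of thickness change. The arithmetic is right, but its premise is assumed.

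**Conclusion.** The concern holds as a gap in standardization together with an inconsistency of method between sections 2 and 4. Following the plan as written can subtract a reading by one method in infiltrated tissue from a reading by another method or in another condition.

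The bias is conditional. It affects the gain within each arm if follow-up conditions differ, and it equals the mean distension present only at baseline, less any present only at follow-up. A change of method adds a shift of unknown direction. That infiltration thickens the tissue, and by how much, is an assumption. For VISTA against sulcular access, a common shift cancels and the expected cost is added noise: 16 to 56% more variance under an assumed SD of 0.4 to 0.5 mm, or 4 to 9% at SD 1.0. The calculations do not show that the sample size is wrong. Thickness is one of several outcomes in a self-described pilot, so the point is moderate and worth correcting because correction is cheap.

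**What to change.** - **Measurement.** Reconcile the Tissue Thickness item, follow-up item 4 and the section 4 outcome so that TT1 and TT2 use one method, one anesthesia condition and one interval before probing, in both arms, at Visit 1 and at visits 5 to 7. The anesthesia procedure itself is for the investigators to settle.
- **Analysis.** Compare 6- and 12-month TT1 and TT2 between arms at patient level with baseline thickness as a covariate, in place of raw change from baseline. Say in the plan that this lessens the effect of baseline error but does not fully remove an arm-specific distortion, because baseline is read after allocation is known.
- **Reporting.** Record the condition of each reading, and report gains within arms with a caution where baseline and follow-up conditions differed. This also serves patients already measured.

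**Cost.** A few sentences, with no added visit. The one downside is that matching the condition may mean local infiltration for the reading at visits 5 to 7, if it is not already given. The analysis change is free.
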